4.3.7 Number and Duration of Contact with Patients

4.3.7.1 CRC Screening

Patients in the Main Trial control arm (ages 50-75) will not be contacted. Patients in the Main Trial intervention arm (ages 50-75) and patients the Sub-study (ages 45-49) intervention arm and comparator arm will receive an Introductory Letter (first contact) that notifies the patient to expect a FIT kit in the mail. This mailing will allow the study team to identify patients with incorrect addresses before mailing the FIT kit.

After mailing the FIT kit (second contact), the study team will make up to two reminder attempts to follow up with patients in the intervention arm (Arm 2) who have not returned a completed FIT kit. If the FIT kit is undeliverable and returned to the study team because of an incorrect address, the patient will be removed from future Reminder Letter mailings.

Main Trial Patients (ages 50-75) in Arm 2 will receive up to two reminder letters (third and fourth contact). All sub-study patients (ages 45-49) in the intervention and comparator arms also will receive up to two reminder letters (third and fourth contact).

For patients who complete a FIT kit and have a negative result: The patient will be notified of the test result by letter (see section 4.3.5).

For patients who complete a FIT kit and have a positive (abnormal) result: The patients' primary care provider or the primary care provider's designee will notify the patient of the results. After the patient is notified of their positive result, the patient navigator (employed by UNC and credentialed by RCCHC and BRH) will contact the patient by phone or, if phone contact is not successful, by mail to offer information and support for accessing follow-up colonoscopy. Communication will include information about no-cost colonoscopy (for uninsured patients) and transportation service to and from the colonoscopy appointment (for all patients). The patient navigator will call the patient up to three additional times to support the patient in scheduling an appointment for a follow-up colonoscopy, preparing for the colonoscopy procedure, accessing transportation, and financial services, and understanding colonoscopy results. The approximate duration of each phone call will be 5-15 minutes.

The total number of contacts initiated by the study team will range from **3** (Introductory Letter + FIT kit mailing + results letter/call) to **9** (Introductory

Letter + FIT kit mailing + up to 2 reminder letters + results letter/call + up to 4 navigation calls for patients with a positive FIT). The study team may have additional contact with patients if the patients reach out to the study team or indicate they require additional contact (e.g., questions or requests for navigation assistance).

4.3.7.2 Provider Surveys

Survey completion will entail a minimum of 2 contacts at each of the 2 time points. The first contact will be a recruitment email and the second contact will be an online survey. Additional contacts may include up to 4 recruitment emails and a brief presentation during a standing provider meeting, to invite participation. The brief survey will require 10 minutes or less.

4.3.7.3 Provider Interviews

Interview completion will entail a minimum of 4 contacts at each of 2 time points. The first contact will be a recruitment email, the second contact will be an interview scheduling call or email, the third contact will be an interview reminder, and the fourth contact will be an interview. Additional contacts may include up to 6 recruitment emails and/or phone calls and a brief presentation during a standing provider meeting, to invite participation. The interview will require approximately 20 minutes.

4.3.7.4 Patient Interviews (applicable to Main Trial participants ages 50-75)

We expect at least 5 contacts including a recruitment letter, a recruitment phone call to schedule the interview, an interview reminder, the interview, and a post-interview contact to mail the gift card. We also will call patients up to 5 times for interview recruitment. Interviews will last approximately 30-45 minutes. Patients aged 45-49 will not be invited to participate in interviews.

4.4 Expected Risks

It is possible that patients may experience emotional distress or feelings of embarrassment of completing a home-based stool test. However, given that CRC screening using FIT is a part of usual care at the participating FQHCs, these risks are not substantially increased as a result of study participation. The letters included with the mailed FIT intervention emphasize the benefits of the screening, that participation is voluntary, they may choose not to answer questions, there will be no effects on care received by the FQHC or providers based on decision about participation, and information collected will be confidential and securely stored.

4.5 Removal of Patients from Protocol

We have not identified any factors *a priori* that would lead the Principal Investigator to remove a patient from the study.

5.0 TIME AND EVENTS TABLE

5.1 Time and Events Table

Main Trial

The timeline of activities for our study is shown in Table 1.

Table 1. Project timeline

Activity	Year and Quarter (Q)											
	Year 1				Year 2				Year 3			
	Q1	Q2	Q3	Q4	Q1	Q2	Q3	Q4	Q1	Q2	Q3	Q4
Round 1												
Identify eligible patients (query EHR)												
Transfer patient data to UNC and REDCap												
Implement mailed FIT outreach (in waves)												
FIT tracking and other data collection												
FIT results notification												
Patient navigation for patients with a positive (abnormal) FIT result												
Provider surveys												
Provider interviews												
Patient interviews												
Round 2												
Identify eligible patients (query EHR)												
Transfer patient data to UNC and REDCap												
Implement mailed FIT outreach (in waves)												
FIT tracking and other data collection												
FIT results notification												
Patient navigation for patients with a positive (abnormal) FIT result												
Provider surveys												
Provider interviews												
Patient interviews												
Outcomes assessment and evaluation												
CRC screening outcomes assessment												
Cost and cost-effectiveness assessment												
Program evaluation												

Sub-study (ages 45-49)

The timeline of activities for the sub-study is shown in Table 1. Participants in the sub-study will only receive one round of mailed FIT outreach because we are in Year 4 of a 6-year award and will not have sufficient time to conduct two rounds of annual FIT with outcome assessment.

Table 2. Substudy Timeline

Activity	Month						
	1	2	3	4	5	6	7
Identify eligible patients (query EHR)							
Transfer patient data to UNC and REDCap							
Randomly assign patients to study arms							
Mail introductory letters							
Mail FIT packets							
Mail reminder letter 1							

Mail reminder letter 2					
FIT results notification					
Patient navigation for patients with a positive FIT result					
FIT tracking and other data collection					
FIT return and CRC screening outcomes assessment					
Program evaluation					

6.0 UNANTICIPATED PROBLEMS

6.1 Definition

As defined by UNC's IRB, unanticipated problems involving risks to study subjects or others (UPIRSO) refers to any incident, experience, or outcome that:

- Is unexpected (in terms of nature, severity, or frequency) given (a) the research procedures that are described in the protocol-related documents, such as the IRB-approved research protocol and informed consent document; and (b) the characteristics of the subject population being studied;
- Is related or possibly related to a subject's participation in the research; and
- Suggests that the research places subjects or others at a greater risk of harm (including physical, psychological, economic, or social harm) related to the research than was previously known or recognized.

6.2 Reporting

Any UPIRSO that occurs during the conduct of this study and that meets all three criteria listed in 6.1 must be reported to the UNC IRB using the IRB's web-based reporting system.

7.0 STATISTICAL CONSIDERATIONS

7.1 Study Design

Main Trial

This study includes a two-arm, multi-center, randomized controlled trial. The primary objective of the trial is to assess the effectiveness of a mailed FIT outreach program on CRC screening completion in a community health center context in both northeastern and western North Carolina, by comparing the proportion of patients screened in the intervention arm to the control arm. Arm 1. Participants receive usual care (no change from the original study protocol). Arm 2. Participants receive the following already IRB-approved intervention components: (1) Introductory Letter to let patients know they should expect a FIT kit in the mail; (2) Cover Letter and FIT kit with instructions; (3) Reminder Letter 1 for patients who have not returned the FIT kit; and (4) Reminder Letter 2 for patients who still have not returned the FIT kit (added in protocol version 2).

The secondary objective of this study is to develop and refine implementation outcomes to inform a large, multi-site implementation study. As part of this secondary objective, our aims are to test the logistical feasibility and patient and provider acceptability of a mailed reminder plus FIT outreach program (Aim 2), and estimate the cost per person screened of the mailed reminder plus FIT outreach program, as well as the level of resource investment required to scale-up the program statewide (Aim 3).

Sub-study (ages 45-49)

Objective 1 of this sub-study is to compare CRC screening rates before and after mailed FIT outreach to patients aged 45-49 in a community health center context in northeastern North Carolina. All participants will receive the same intervention components as are described above for the Arm 2 in the Main Trial: 1) introductory letter to let patients know they should expect a FIT kit in the mail; 2) cover letter and FIT kit with instructions; 3) reminder letter 1 for patients who have not returned the FIT kit; and 4) reminder letter 2 for patients who still have not returned the FIT kit.

Objective 2 of this sub-study is to assess the impact of varying FIT packet appearance on FIT return. Patients will be randomized to receive FIT materials in either a: 1) padded envelope with a sticker message (e.g., “Important information from your doctor”) and a United States Postal Service tracking label, or 2) plain white envelope without a sticker message or tracking label. We will compare the proportion of participants in each arm who complete a FIT.

7.2 Sample Size and Accrual

Main Trial

Our project funding supports a sample size of up to 4,000 patients at two clinical sites who are eligible for CRC screening. Using a 1:1 randomization approach, up to 2,000 RCCHC patients and up to 2,000 BRH patients will be randomized to the two study arms. For each FQHC, up to 1,000 patients will be randomized to each of the two arms. Our statistician performed formal power calculations for our primary study outcome comparing CRC screening completion for the intervention arm vs. the control arm, stratified by patient insurance status (4 strata: Medicare, Medicaid, commercial/private, and self-pay/other). Based on previous research, we anticipate that 25% of those receiving the intervention will complete CRC screening, and 17% of patients in the usual care arm will complete screening (8% difference between arms). We need 492 participants per arm, per strata to have at least 80% power to detect an 8% difference between study arms at 1-sided alpha level 0.0125 (3,936 participants total, which can be rounded up to 4,000). We calculated power by SAS PROC Power (SAS Institute, Cary, NC).

Sub-study (ages 45-49)

Sample size in this additional substudy is determined by feasibility and resource constraints. We have the resources to do intervention testing in this new age group (45-49) in a single clinic site. We will identify the cohort of participants who are eligible for screening on a given index date. We estimate 500 patients are in this age group and eligible for screening. We estimate that approximately 10%, i.e., 50 individual patients, will be current with screening at baseline. We will conduct the mailed intervention on the approximately 450 patients who are not current and then assess the screening rate at 60 days in same cohort. For outcome 2, we will use a 1:1 randomization approach to randomize patients the patients who are not current with screening to the two experimental study arms (envelope type).

Our statistician performed formal power calculations for our study outcomes of change in CRC screening rate (pre-post) for this age group, as well as FIT return compared across the two arms. **Outcome 1:** We will observe baseline and post-intervention status of CRC for subjects who are not screened at baseline. For those who screened at baseline, we will not observe post-intervention CRC status, but we assume a high post-intervention screen rate for such subjects if they receive intervention before they receive screening. This leads to a paired binary data problem, and we test if the conversion rate (from not screened to screened) is high enough. A sample size of 500 achieves 80% power to detect an odds ratio of 2.922 using a two-sided McNemar test with a significance level of 0.05. This calculation is based on a difference between two paired proportions of 0.034 (P10-P01), where P10 (about 0.052) refers to the proportion of subjects who not screen at baseline but screen after intervention and the proportion (P01) of screen at baseline but not screen after intervention. This is an assumed number because we are not able to observe it but assume it's a very small number) is 0.018. The proportion of discordant pairs is 0.07. We will report baseline screening rate and post-intervention screening rate. **Outcome 2:** With 225 patients per arm, we reach 80% power, with 1-sided alpha 0.05, to detect a difference between the group FIT mail back rates of 0.102. The FIT mail back rate in Group 1 (the treatment group) is assumed to be 0.20 under the null hypothesis and 0.302 under the alternative hypothesis. The rate in Group 2 (the control group) is 0.20. We calculated power using SAS PROC Power (SAS Institute, Cary, NC).

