7.3 Data Analysis Plans

Main Trial

Our main statistical test for primary and secondary outcomes will be a Mantel-Haenszel chi-squared test, adjusted for recruitment site (FQHC). If there are important differences between the control and intervention arms across baseline variables known to be associated with the outcome being tested, we will also then use multiple logistic regression, adjusting for the additional baseline variables. One-sided tests will be used for the primary and secondary outcomes because we expect active interventions will lead to more favorable results compared to usual care.

7.3.1 Aim 1

For Aim 1, the main outcome of interest is the proportion of the sample completing FIT kits among those to whom the materials are mailed. We refer to this metric as the “proportion screened.” Using a 1:1 randomization approach, up to 2,000 RCCHC patients and up to 2,000 BRH patients will be randomized to each study arm (Arm 1-usual care; Arm 2-introductory letter + mailed FIT + 2 follow-up reminder letters).

Aim 1 analytic approach: Our primary analysis will be a crude comparison of proportions of completed CRC screening at 6 months post-FIT mailing for the mailed FIT plus reminder arm vs. the usual care arm using a one-sided Mantel-Haenszel chi-squared test, controlling for recruitment site (FQHC) and insurance status. As stated in the overview, we will also, if necessary, conduct a multiple logistic regression analysis. We will also compare the proportion screened between the mailed FIT plus reminder arm vs. the usual care arm for each of the four insurance status groups, using a one-sided Mantel-Haenszel chi-squared test, controlling for recruitment site, conducted at the 0.0125 significance level.

7.3.2 Aim 2

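### Cheap improvement: Holm's step-down in place of a fixed one-sided 0.0125 for the four insurance-group tests would raise per-group power from 80% to as much as 90%, at the same family error

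*Combined protocol and SAP*

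**What the plan says.** Section 7.2 (Main Trial) bases its power calculation on insurance status, with four strata. It assumes 25% screening completion with the intervention and 17% with usual care. It then asks for 492 participants per arm per stratum "to have at least 80% power to detect an 8% difference between study arms at 1-sided alpha level 0.0125", which gives 3,936 in total, rounded up to 4,000.

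Section 7.3.1 (Aim 1) names one overall comparison as the primary analysis: a one-sided Mantel-Haenszel test controlling for site and insurance status. No significance level is given for it. The section then adds a comparison "for each of the four insurance status groups, using a one-sided Mantel-Haenszel chi-squared test", "controlling for recruitment site, conducted at the 0.0125 significance level". The opening of section 7.3 confirms the direction: "One-sided tests will be used for the primary and secondary outcomes".

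No step-down, closed-testing or gatekeeping procedure is described. The plan uses neither the word Bonferroni nor a stated family-wise level for these tests.

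**The concern.** Four tests each held to 0.0125 is what a single-step Bonferroni split of 0.05 produces. Holm's procedure gives the same guarantee on the family error, also without any assumption about dependence between tests, and it rejects everything that the fixed threshold rejects. When several groups truly benefit, the fixed threshold therefore misses some group-level findings that Holm would make from the same data.

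What is at stake is how many insurance groups the trial can individually show to benefit. These are the comparisons on which section 7.2 computes its sample size, so their power matters to the design. The overall conclusion on effectiveness is not at stake.

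**Working it through.** **Inputs.** From 7.2: 25% v 17%, 492 per arm per stratum, four strata, one-sided 0.0125, at least 80% power. From 7.3.1: four one-sided tests, each at 0.0125. The family level of 0.05 is inferred: 4 × 0.0125 = 0.05.

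**1. The plan's own figure.** Use the two-proportion formula with pooled variance under the null and no continuity correction. The mean rate is (0.25 + 0.17)/2 = 0.21, and the normal quantiles are 2.2414 (one-sided 0.0125) and 0.8416 (80% power).

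n = [2.2414 × √(2 × 0.21 × 0.79) + 0.8416 × √(0.25 × 0.75 + 0.17 × 0.83)]² / 0.08²
= [2.2414 × 0.5760 + 0.8416 × 0.5732]² / 0.0064
≈ 491.5, rounded up to 492.

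Then 492 × 2 × 4 = 3,936. The stated figures reproduce, and power at 492 is 80.05%.

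**2. Family error with the fixed threshold.** For four independent groups with no effect anywhere, it is 1 − (1 − 0.0125)⁴ = 0.0491.

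**3. Holm's thresholds.** Order the one-sided p-values from smallest to largest and compare them with 0.05/4 = 0.0125, 0.05/3 = 0.0167, 0.05/2 = 0.025 and 0.05/1 = 0.05, stopping at the first failure.

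**4. Comparison by simulation.** 400,000 trials per scenario; four independent groups of 492 per arm; binomial counts; pooled one-sided z-tests. Site stratification within each group is ignored and no dropout is applied. Effective groups have 25% v 17%, and the others have 17% in both arms.

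| Groups with the effect | Power per effective group, fixed 0.0125 | Power per effective group, Holm | Family error, fixed | Family error, Holm |
|---|---|---|---|---|
| 4 | 80.2% | 90.4% | none possible | none possible |
| 3 | 80% | 86% | 1.3% | 4.1% |
| 2 | 80% | 83% | 2.5% | 4.4% |
| 1 | 80% | 80% | 3.7% | 4.7% |
| 0 | – | – | 4.9% | 4.9% |

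When all four groups have the effect, all four are significant in 41.5% of trials with the fixed threshold and 72.0% with Holm. The expected number of significant groups is 4 × 0.802 = 3.21 v 4 × 0.904 = 3.62. Holm lost no rejection that the fixed threshold made.

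**5. Sensitivity.**
- A 5-point effect in all four groups gives 40% v 47% per group.
- If the intended family level were one-sided 0.025, so that the fixed threshold was 0.025/4, per-group power would be 72% v 83% with the 8-point effect in all groups.
- The documents give no insurance mix. With an assumed split of 700/300/500/500 per arm and all groups effective, power is 93/57/81/81% fixed and 97/75/90/90% with Holm.

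**6. The overall primary test.** At 1,968 per arm (4 × 492), its power is above 99.9% even at one-sided 0.0125. Holm on the group tests does not touch it.

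**The case against.** The strongest reply is that nothing here is wrong. The threshold is pre-specified, consistent between 7.2 and 7.3.1, valid, and delivers the power the plan promises. The group comparisons are additional to the stated primary analysis, and no section makes significance in all four groups a success criterion. A fixed level also lets each group's result stand alone, with simple simultaneous confidence intervals. All of this stands, and it makes the point an efficiency suggestion.

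Three stronger readings are tempting, and the documents do not support them.

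- A reader might infer that Holm delivers 90% per group whatever happens. That figure needs the 8-point effect in all four groups. The gain shrinks as fewer groups benefit and is negligible if only one does. Group-level tests are of most interest when effects may differ, which is where Holm helps less.
- A reader might infer that the extra power is free. When three groups benefit and the fourth does not, the fourth's chance of a false claim rises from 1.25% to about 4.1%. That is within the 5% family level but more than three times as high.
- A reader might infer that the whole of Aim 1 is then protected at 5%. The plan gives the overall test neither a level nor a place in the testing order, so the family covers only the four group tests.

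Nor does the sample size rest on these tests alone: 7.2 opens by saying that funding supports up to 4,000 patients.

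**Conclusion.** The point holds as an inexpensive improvement to a valid plan. On the plan's own assumptions (equal groups of 492 per arm, 25% v 17% in every group), Holm raises per-group power from 80% to about 90%. With three, two or one effective groups it gives 86%, 83% and 80%. Power is never below that of the fixed threshold, and simulated family error stayed at or below 4.9%.

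The simulated power figures assume independent groups; Holm's error control does not need that assumption. The 5% one-sided family level is an inference from 0.05/4, but the advantage does not depend on it.

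**What to change.** Make the change before any group results are seen, since a later switch would look data-driven.

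- **7.3.1:** replace the fixed 0.0125 with Holm's procedure. Order the four one-sided p-values, compare them in turn with 0.0125, 0.0167, 0.025 and 0.05, and stop at the first failure. If another family level is intended, use that level divided by 4, 3, 2 and 1. State the family level, and state that the family consists of the four insurance-group tests.
- **7.2:** say that 80% per group at 0.0125 is a lower bound under the planning assumptions. Keep the sample size.

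The cost is two short edits, with no new patients, data or procedures. Besides the higher false-claim chance for a lone null group, the sponsor accepts that each group's threshold depends on the other groups' p-values and that simultaneous intervals matching Holm are harder to give. Ordinary per-group intervals can still be reported. A sponsor who prefers standalone group conclusions could reasonably keep the fixed level, and should then say so.

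### Sub-study Outcome 1 is powered for a McNemar test that the planned data cannot supply, and 7.3.4 names a Mantel-Haenszel test without stating pairing

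*Combined protocol and SAP*

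**What the plan says.** Section 7.2 expects about 500 patients aged 45-49 at one clinic, about 50 of them current with screening at baseline. The other 450 or so are mailed a FIT, and the investigators will "then assess the screening rate at 60 days in same cohort". The power statement reads: "A sample size of 500 achieves 80% power to detect an odds ratio of 2.922 using a two-sided McNemar test", at a significance level of 0.05. Its inputs are P10 of about 0.052 (not screened, then screened), P01 of 0.018 (screened, then not) and a discordant proportion of 0.07.

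Of the patients already screened, the section says: "For those who screened at baseline, we will not observe post-intervention CRC status". It continues that "we assume a high post-intervention screen rate for such subjects if they receive intervention before they receive screening". Of P01 it says: "This is an assumed number because we are not able to observe it". It then promises: "We will report baseline screening rate and post-intervention screening rate".

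Section 2.2 describes the objective as a comparison of the proportion current before outreach with the proportion current within 60 days of mailing, from an EHR query. Section 7.3.4 gives one main test for both sub-study outcomes, a Mantel-Haenszel chi-squared test. It does not mention pairing, strata, sidedness or alpha. It adds a logistic regression if the arms differ at baseline.

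**The concern.** There are three linked gaps.

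- **The missing cell.** McNemar's test uses only the two discordant counts. One of them will not be collected, and the plan does not say whether the analyst should enter 9 (0.018 of 500), zero or something else. Nor is it clear what P01 means. It could be actual lapse over 60 days, or what screened patients would have done had outreach reached them first. No data can supply the second.
- **The post-intervention rate.** A rate on all 500 needs the status of the same 50 patients.
- **The named test.** Section 7.3.4 does not carry the pairing over from 7.2. Its adjustment for differences between arms has no meaning for a single group measured twice, so it can apply only to Outcome 2.

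Near the design effect, two analysts who both follow the plan could therefore report different p-values. At any effect size they could report different post-intervention rates.

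**Working it through.** **Inputs from 7.2:** n = 500; odds ratio 2.922; discordant proportion 0.07; two-sided alpha 0.05; 50 current and 450 not current at baseline; control-arm FIT return assumed for Outcome 2 ("The rate in Group 2 (the control group) is 0.20").

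**1. The plan's own figure.** P01 = 0.07/(1 + 2.922) = 0.0178 and P10 = 0.07 − 0.0178 = 0.0522. The number of discordant pairs is Binomial(500, 0.07). Given m discordant pairs, conversions are Binomial(m, P10/0.07), tested by the exact two-sided binomial test against 1/2. Power is 80.0%, as stated. With the rounded 0.052 and 0.018 it is 79.2%.

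**2. Power as the unobserved cell varies** (P10 = 0.052, n = 500):

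| P01 | Patients | Exact power |
|---|---|---|
| 0.012 | 6 | 94% |
| 0.018 | 9 | 79% |
| 0.024 | 12 | 57% |
| 0.030 | 15 | 35% |

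**3. The p-value as the fill varies.** With b conversions and c lapses (b > c), exact p = 2 × P(X ≤ c), X ~ Binomial(b + c, 1/2). The design value is b = 0.052 × 500 = 26.

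| b | c | p |
|---|---|---|
| 26 | 0 | < 0.001 |
| 26 | 9 | 0.006 |
| 26 | 12 | 0.034 |
| 26 | 13 | 0.053 |
| 73 | 50 | 0.047 |
| 90 | 50 | 0.0009 |

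So from 73 conversions (73/450 = 16.2%) the result is significant even if all 50 lapse. At the 20% return assumed for Outcome 2, conversions would be 0.20 × 450 = 90.

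**4. Filling the cell with zero.** With c = 0, p = 2 × 0.5^b: 0.0625 at b = 5 and 0.031 at b = 6. Six of 450 is 1.3%. The documents give no background rate for ages 45-49. At assumed 60-day backgrounds of 1%, 2% and 3% with no outreach effect, P(b ≥ 6) with b ~ Binomial(450, background) is 30%, 89% and 99%. The nearest figure in the plan is 17% usual-care completion, for ages 50-75 over 6 months. If that applied here at a constant hazard (both assumptions), the 60-day rate would be 1 − 0.83^(60/182.5) = 5.9%, or about 27 of 450. That is about the 26 conversions in the design.

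**5. The 7.3.4 test read literally.** On the planned counts the baseline rate is 50/500 and the later rate is (50 − 9 + 26)/500 = 67/500. McNemar gives (26 − 9)²/(26 + 9) = 8.26, p = 0.004. Mantel-Haenszel stratified by subject gives the same 8.26. Unpaired Mantel-Haenszel gives 2.79, p = 0.095. Simulating paired data from the planned cells (0.052, 0.018, 0.082, 0.848) and applying the unpaired chi-squared test gives power of about 31%.

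**6. The reported rate.** On all 500 it is (50 − c + b)/500. At b = 90 this is 28.0% with c = 0, 26.2% with c = 9 and 18.0% with c = 50.

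**The case against.** The plan's power arithmetic is correct. A reader might infer a miscalculated sample size, but nothing supports that. In any case the plan says: "Sample size in this additional substudy is determined by feasibility and resource constraints".

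A reader might also infer that 7.2 and 7.3.4 flatly contradict each other. They need not. Section 7.2 treats Outcome 1 as paired, and Mantel-Haenszel stratified by subject is McNemar's test. This stands as a possible reconciliation, but 7.3.4 does not state it and the missing cell would remain. The 31% figure holds only for the unpaired reading.

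Next, 7.2 does supply a value, 9 of 500, and calls it very small. At 26 conversions every fill from 0 to 12 is significant, and if FIT return is near 20% the fill cannot change significance. Both points stand. They narrow the p-value concern to effects near the design value. They do not turn a planning assumption into an analysis rule. The lower end of the 18% to 28% range is an extreme bound, since all 50 lapsing in 60 days is not realistic. Between 0 and 9 lapses the range is 26.2% to 28.0%.

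Finally, the 60-day rate in 7.2 may be meant for the 450 alone, because that phrase follows directly on them, and criterion 3.1.3 excludes patients who are current. That reading is fair, and it is the one the fix adopts. It does not fit a McNemar test on 500 pairs.

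**Conclusion.** The concern holds in a limited form. The 80% figure is right for its inputs, but one input is a cell the plan says it will not observe, so the powered test cannot be run on the planned data. Moving that cell from 9 to 12 patients takes power from 79% to 57%. Setting it to zero makes 1.3% conversion significant. Section 7.3.4 leaves pairing unstated and carries an adjustment that fits only Outcome 2.

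It would go too far to conclude that Outcome 1 is uninterpretable. At 73 or more conversions significance is settled whatever the fill, and the conversion proportion among the 450 is observed in the planned data. Rejection would still not show that outreach caused the screening, because there is no concurrent control. The documents do not hide this; they describe a before/after comparison.

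The power and p-value figures assume the exact two-sided McNemar test, apart from the chi-squared comparison in step 5. The background rates are illustrations, not figures for this age group. Enrolment, the main trial and the randomised Outcome 2 are unaffected.

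**What to change.** **Main option.** In 7.2 and 7.3.4, with matching wording in 2.2 and 7.1:

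- Define Outcome 1 as the proportion completing any CRC screening within 60 days of FIT mailing among the approximately 450 patients not current at baseline, with an exact (Clopper-Pearson) 95% confidence interval.
- Replace the McNemar power statement with precision: 26/450 = 5.8% (3.8% to 8.4%); 90/450 = 20% (16.4% to 24.0%).
- Describe the result as an uncontrolled single-group estimate. The baseline rate in these patients is zero by definition, so this is not a before/after comparison, and the descriptions in 1.1 to 1.3 should agree.
- Limit the adjustment for differences between arms to Outcome 2.
- If a post-intervention rate on all 500 is also reported, state how the roughly 50 are counted and show the range.

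**If a paired test is kept.** Name McNemar, or Mantel-Haenszel stratified by subject, in 7.3.4. State that P01 is actual 60-day lapse, and obtain the 60-day EHR status of the roughly 50 patients. If P01 is meant as a hypothetical response, no data can fill it and the paired test should be dropped.

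**Cost.** The main option is wording only, with no extra patients or data. Its downside is that Outcome 1 becomes an estimate and not a pass/fail test. The paired option adds about 50 record checks. It may also need added data access or IRB approval, because these patients fall outside the enrolled cohort: the manual review in 4.3.6 covers participants' records, and the consent waiver in 8.1 covers mailed outreach participants.
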